##### *Dabigatran etexilate pellets:*

- Substance: Dabigatran etexilate
- Pharmaceutical formulation: pellets
- Source: Boehringer Ingelheim Pharma GmbH & Co. KG, Germany
- Unit strength: pellets stick packs to be sprinkled on food (for the available strengths please refer to the nomogram in [Appendix 10.4.1](#)). Detailed preparation and administration instructions will be included in the ISF.
- Total Daily dose: The administered dose (b.i.d.) is based on an age and weight adjusted nomogram included in [Appendix 10.4.1](#). This nomogram has been generated to estimate a yield and exposure comparable to the exposure observed in previously completed adult VTET/sVTEp and AF populations
- Route of administration: p.o.
- List of excipients: The most up to date list will be provided in the ISF

**Proprietary confidential information.**

© 2019 Boehringer Ingelheim International GmbH or one or more of its affiliated companies. All rights reserved.

This document may not - in full or in part - be passed on, reproduced, published or otherwise used without prior written permission.

*Dabigatran etexilate oral liquid formulation:*

- Substance: Dabigatran etexilate granules (180.4 mg) and flavoured or unflavoured solvent for reconstitution (28 ml)
- Pharmaceutical formulation: oral liquid formulation
- Source: Boehringer Ingelheim Pharma GmbH & Co. KG, Germany
- Unit strength: Granules for oral solution (6.25 mg/mL after reconstitution)
- Total Daily dose: A specific volume of a 6.25 mg/mL solution after reconstitution is administered (b.i.d.) based on an age and weight adjusted nomogram included in [Appendix 10.4.1](#). This nomogram has been generated to estimate a yield and exposure comparable to the exposure observed in previously completed adult VTEt/sVTEp and AF populations, particularly in patients whose observed exposure was generally associated with the most favourable balance between efficacy and safety.
- Route of administration: p.o.
- List of excipients: The most up to date list will be provided in the ISF.

#### **4.1.2 Method of assigning patients to treatment groups**

After obtaining signed informed consent and if applicable assent, patients should complete the screening (Visit 1) procedures and laboratory assessments. Inclusion and exclusion criteria should be assessed to ensure inclusion of eligible patients. The unresolved clinical risk factor requiring longer duration anticoagulation for the secondary prevention of VTE must be specified at screening (e.g. central venous line).

All eligible patients who fulfil all inclusion and exclusion criteria will be assigned to receive dabigatran etexilate. Patients assigned to OLF will be randomized based on 1:1 ratio to receive flavoured or unflavoured solvent for reconstitution. The correct trial medication kit assignment will be managed by Interactive Response Technology (IRT) based on the estimated dose - see [Section 4.1.3](#). All necessary instructions for using the IRT system will be described in a user guide / manual, a copy of which will be available in the ISF. In this trial, IRT will be used for medication assignments (including dose adjustments) and to control aspects of the medication supply chain.

Recruitment will first be initiated in the adolescent group (12 yrs. to <18 yrs.) and may be consecutively opened to younger age groups (2 to <12 years of age); and then to the youngest patients (0 to <2 yrs.) based on the DMC recommendations.

#### **4.1.3 Selection of doses in the trial**

Estimated doses for paediatric patients assigned to take dabigatran etexilate will be based on age and weight according to a nomogram (please refer to [Appendix 10.4](#)). Patients able to swallow capsules (aged  $\geq$  8 years) will be assigned to take capsules. If a patient aged  $\geq$  8

**Proprietary confidential information.**

© 2019 Boehringer Ingelheim International GmbH or one or more of its affiliated companies. All rights reserved.

This document may not - in full or in part - be passed on, reproduced, published or otherwise used without prior written permission.

years but below 12 years of age is unable to take capsules, they will be assigned to take the pellets sprinkled on food. Patients < 8 years of age are scheduled to receive pellets sprinkled on food. OLF may be used for patients who are < 12 months of age. For patients < 12 months of age OLF is preferred over pellets provided that OLF supplies are available to the site.

Switching between different dabigatran etexilate formulations during the study is not recommended, but could be considered in special cases following discussion with the Sponsor, provided that the steady state has been reached with the currently assigned formulation (i.e. at least 6 consecutive dabigatran etexilate doses have been taken). A titration visit should be performed 3 days (6 consecutive dabigatran etexilate doses are taken) after the formulation switch.

The dose of dabigatran etexilate must be adjusted throughout the study period to ensure that a steady state plasma concentration between 50 and < 250 ng/mL is achieved. Assigned dosing in this study will be intended to target plasma dabigatran concentrations that have generally been proven to be safe and effective in multiple adult populations. The dose regimen will be reviewed on an ongoing basis by the DMC and can be further revised as data on trough dabigatran levels and safety and efficacy data are obtained.

Dose selection is based on dabigatran's linear PK ([U09-2262-01](#)) and renal function (glomerular filtration rate (GFR)) being the most important determinants of dabigatran PK.

Allometric models are considered appropriate in determining drug doses in paediatrics ([R08-4306](#)). In order to adjust for the on average lower body weight and hence lower absolute glomerular filtration rate in children aged below 1 year, the dose estimation procedure according to Hayton ([R06-2299](#)) seems appropriate. Hayton's model characterized the maturation and growth of renal function parameters based on data obtained from 63 healthy children between the ages of 2 days and 12 years.

For renally eliminated drugs like dabigatran, this model can be used to estimate dosing regimens based on the adult dose and adjusted to the age and weight of the child. In this way, doses and resulting nomograms can be used in clinical practice without the need for regular laboratory measurements.

Compared to the adult VTE study RECOVER (mean age 55.0), the general paediatric population is characterized by better renal function. To yield total dabigatran exposure at trough comparable to the trough exposure observed in the adult VTE program (i.e. RECOVER: dose 150 mg BID) and to be able to scale down the doses for the paediatric population within the confines of Hayton's model (i.e., GFR predictions up to age of 20 years, at which normal GFR is assumed to be 136 mL/min), a 20 year old adult reference patient weighing 70 kg was chosen. Since this reference patient is younger and has a higher dabigatran clearance due to the better renal function, the dose of 150 mg BID would result in an average trough exposure lower than the trough exposure seen in RE-COVER.

Therefore, this reference patient would receive higher dabigatran etexilate doses, i.e. 300 mg dabigatran etexilate BID or 4.3 mg/kg dabigatran etexilate BID and doses are scaled down to paediatric doses accordingly (fractional dose).

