### 3.3.4 Removal of patients from therapy or assessments

#### 3.3.4.1 Removal of individual patients

An individual patient is to be withdrawn from the trial if:

- The patient / parent / legal guardian withdraws consent, without the need to justify the decision.

An individual patient is to be discontinued from trial treatment, but will remain part of the study and analysis population:

- If the patient is no longer able to take trial medication for other medical reasons (e.g. surgery, AEs, other diseases or concomitant therapies).
- If the patient is noncompliant with study drug administration despite all possible efforts.
- If, in the opinion of the Investigator, continuation on the study drug is not in the patient's best interest, if eligibility criteria are being violated, or if the patient fails to comply with the protocol (e.g. non-attendance at trial assessments).
- In the event that a recurrent thromboembolic event as assessed by appropriate imaging modalities is observed or if the patient experiences a drug-related significant or drug-related serious AE or if drug toxicity is observed.
- If the patient does not reach a total dabigatran plasma trough concentration within the pre-specified therapeutic range after one dose adjustment.
- If the patient becomes pregnant or a pregnancy is suspected during the trial the patient will be discontinued from the dabigatran treatment and will be put on an appropriate therapy per investigator judgment. The patient will be followed up until the end of the study and until the birth or otherwise termination of the pregnancy. For further information, including the process for follow up on the outcome of the pregnancy please see [Section 5.2.2.2](#).
- If a patient develops an active meningitis, encephalitis, or intracranial abscess.

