**Proprietary confidential information.**

© 2019 Boehringer Ingelheim International GmbH or one or more of its affiliated companies. All rights reserved.

This document may not - in full or in part - be passed on, reproduced, published or otherwise used without prior written permission.

- If the patient develops renal dysfunction anytime during the course of the study (eGFR < 50 mL/min/1.73m^2 using the Schwartz formula, confirmed by one retesting within the next 14 calendar days). If a patient develops eGFR < 50 mL/min/1.73m^2 using the Schwartz formula for a second time during the course of the study, treatment with dabigatran etexilate must be stopped without further retesting
- If the patient does not require treatment with anticoagulants any longer due to resolution of the underlying clinical risk factor prior to 12 months of planned anticoagulation treatment. In such cases, an early EOT Visit is to be performed and the patient should still be followed up according to the remaining visit schedule until the end of the study.

In order to protect patient safety, measurements of dabigatran trough plasma levels will be performed in a central laboratory

If a patient has a dabigatran plasma level of < 50 ng/mL or ≥ 250 ng/mL confirmed despite a dose adjustment, they will be discontinued from trial treatment and must be switched to an appropriate alternative therapy at investigator's discretion.

Dabigatran is predominantly excreted by the kidney; special attention should be given to the kidney function of these patients when needed. As stated above, any patient with confirmed eGFR < 50 mL/min/1.73m^2 using the Schwartz formula at any time during the treatment period will be discontinued from trial treatment. Any suspected worsening of renal function during the study should be investigated by eGFR evaluation.

Patients who discontinue study drug or withdraw from the trial after being entered (Visit 2) will be considered as “early discontinuations” and will not be replaced. The reason for premature discontinuation must be recorded in the eCRF. The data will be included in the trial database and will be reported.

Patients who discontinue study drug prior to 12 months of planned treatment due to resolution of the underlying clinical risk factor will not be considered as “early discontinuations”.

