**Proprietary confidential information.**

© 2019 Boehringer Ingelheim International GmbH or one or more of its affiliated companies. All rights reserved.

This document may not - in full or in part - be passed on, reproduced, published or otherwise used without prior written permission.

Table 4.1.3: 2 Summary of dose adjustments based on trough dabigatran plasma concentration

Steady State Dose Range	Corresponding Action
Between 50 and < 250 ng/mL	Continue on same dose
Less than 50 ng/mL	Dose may be increased by 10-100%. Maximal allowed single dose in this study is 330 mg.
Greater than or equal to 250 ng/mL	Dose may be reduced by 25-50%

The reduction of a dose is not expected to result in concentrations < 75 ng/mL, but should be sufficient to avoid high concentration of  $\geq 250$  ng/mL. Blood sampling to measure trough dabigatran concentration (derived from dTT or alternative method) will be repeated at least 3 days (after at least 6 adjusted consecutive dabigatran etexilate doses have been taken), but no later than 6 days after dose adjustment, to confirm the new dose. After dose adjustment, the total dabigatran trough concentration should be between 50 and < 250 ng/mL.

If a patient cannot reach trough plasma concentrations between 50 and < 250 ng/mL after one dose adjustment, they must discontinue the study medication.

Due to the dabigatran etexilate limit of 22.2 mg/kg/day (based on excipient acceptable daily intake) as well as the maximal dabigatran etexilate single dose of 330 mg, up-titration will not be feasible in all instances. Likewise down-titration will not be possible in all cases due to unavailability of required dosages, see [Appendix 10.4.2](#). Affected patients have to be discontinued from dabigatran etexilate once the defined plasma trough concentration between 50 and < 250 ng/mL is not reached.

During the course of the study, the DMC can recommend further refinement of the target therapeutic trough steady state dabigatran concentrations based on data from ongoing paediatric studies or if emerging data from other dabigatran etexilate studies in other populations suggest that wider or narrower total dabigatran trough concentration range is associated with better benefit / risk ratio.

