## 5.7 PHARMACODYNAMICS

### 5.7.1 Pharmacodynamic endpoints

Determination of the exploratory pharmacodynamic parameters dTT (Anti-Factor IIa activity), aPTT and ECT will be performed in this trial. Diluted thrombin time (dTT) or alternative registered method / assay (where available and after consultation of the Sponsor) will be employed for the quantitative measurement of dabigatran concentrations for dose adjustment. The analysis of dTT will be done by a central laboratory. Diluted TT may also be analysed by a local laboratory, if feasible. The dabigatran etexilate dose administered to patients may be adjusted upon dabigatran plasma level measurement from Visit 3 or other future visits as needed to achieve the target plasma range, based on the assessment of dabigatran plasma levels. Further, alternative coagulation assays for dabigatran, e.g. ecarin based tests, may be explored.

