### 7.3.2 Secondary analyses

Secondary analyses are planned for occurrence of post-thrombotic syndrome (PTS), number of dabigatran etexilate dose adjustments (i.e. Number of patients with dabigatran dose adjustments) and pharmacodynamic assessments at Visit 3 (after at least six consecutive dabigatran etexilate doses) and after at least 3 days following any dabigatran etexilate dose adjustment.

- Occurrence of PTS will be summarized by K-M estimate of time to first occurrence. The K-M rate and descriptive rate at 6 and 12 month will be calculated. Early drop out, lost-to-follow-up and death will be considered as non-event and censored.
- Frequency of dabigatran etexilate dose adjustments will be summarized descriptively. This refers to the number of patients with dabigatran etexilate dose adjustment during treatment period because each patient is allowed to have only one dose adjustment.
- pharmacodynamic analyses details can be found in [Section 7.3.5](#) and [7.3.6](#).

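### Sections 4.1.3 and 5.7.1 call for dose adjustment over the whole study while 7.3.2 caps it at one per patient, leaving later drift unresolved and the dose-adjustment endpoint resting on the cap

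*Protocol*

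**What the plan says.** All of the following is in the current protocol text, not only in its amendment log.

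- **Ongoing adjustment.** Section 4.1.3: "The dose of dabigatran etexilate must be adjusted throughout the study period", with the aim of a steady-state concentration of 50 to below 250 ng/mL. Section 5.7.1: the dose "may be adjusted upon dabigatran plasma level measurement from Visit 3 or other future visits as needed to achieve the target plasma range". Treatment lasts up to 12 months. The Flow Chart samples troughs from Visit 3 to Visit 11 and weighs the child at every visit.
- **An explicit cap.** Section 7.3.2: "each patient is allowed to have only one dose adjustment".
- **Stop rules.** Section 3.3.4.1 discontinues treatment in this case: "If the patient does not reach a total dabigatran plasma trough concentration within the pre-specified therapeutic range after one dose adjustment". Sections 4.1.3 and 6.2.2 say of patients who cannot reach the range: "after one dose adjustment, they must discontinue the study medication". A second sentence in 3.3.4.1 is looser; it covers levels outside the range "confirmed despite a dose adjustment, they will be discontinued from trial treatment".
- **The endpoint.** Section 5.2.1 names the number of dose adjustments as a secondary endpoint and explains it as the number of patients adjusted. Section 7.3.2 gives the cap as the reason the two are the same.

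**The concern.** The stop rules in 4.1.3 and 6.2.2, and the first in 3.3.4.1, describe a patient who never gets into range. They do not clearly describe a patient who is adjusted once, is confirmed in range, and leaves it months later. For that patient one passage requires a change, another permits it and a third forbids it. Sites could then handle identical patients differently, which affects who remains on drug in a safety trial.

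The endpoint inherits the problem. The number of adjusted patients equals the number of adjustments only if nobody is adjusted twice. If a site follows 4.1.3 or 5.7.1 and adjusts again, the endpoint as explained does not register it.

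**Working it through.** **1. The passages applied to one patient.** Take a child adjusted after Visit 3, confirmed in range at the Titration Visit, and below 50 ng/mL at a later visit.

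| Section | Instruction for this child |
|---|---|
| 4.1.3 (aim) | Adjust |
| 5.7.1 | May adjust, as needed |
| 7.3.2 | No second adjustment allowed |
| 4.1.3, 6.2.2, and first rule in 3.3.4.1 | Written for failure to reach range; this child did reach it |
| 3.3.4.1, looser sentence | Could mean stop, if the earlier adjustment counts |

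Reading the limit as one adjustment per excursion would remove the conflict, but 7.3.2 sets it per patient.

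**2. Reproducing the dose equation (4.1.3).** Dividing the stated GFR equation by weight and by 136/70 = 1.94 mL/min/kg gives 8.14/1.94 = 4.196 and (8.14 − 2.60)/1.94 = 2.856. The reference dose is 300/70 = 4.29 mg/kg. These agree with the stated 4.20, 2.85 and 4.3 up to rounding. The single dose in mg is therefore

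D(age, W) = 4.3 × W^0.662 × (4.20 − 2.85 e^(−0.0822 × age)), with age in months and W in kg.

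**3. Rise in calculated dose over 12 months.** The weights are assumptions; the protocol gives none. New patients need at least 3 months of prior treatment, so entry from birth is not considered.

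- 3 months, 6 kg: 4.3 × 3.274 × 1.973 = 27.8 mg. 15 months, 10 kg: 4.3 × 4.592 × 3.370 = 66.5 mg. The ratio is 2.40 before rounding of the doses.
- 3 months, other assumed weights: 5 to 8.5 kg gives 2.43, and 7 to 12 kg gives 2.44.
- 6 months: 6 to 9 kg gives 1.89, 7.5 to 10.5 kg gives 1.80, and 9 to 12.5 kg gives 1.79.
- 12 months: 1.41 to 1.42. 24 months: 1.18 to 1.21. 8 or 12 years: 1.07 to 1.10.

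**4. What this means for the trough.** Take exposure as proportional to dose over renal clearance, in line with the linear kinetics and renal elimination the protocol describes. On an unchanged dose, the starting trough needed to be at 50 ng/mL or above after 12 months is 50 × ratio: about 120 to 122 ng/mL for entry at 3 months, and about 90 to 94 for entry at 6 months. Lower starting troughs would drift below range.

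**5. Does one permitted step cover the growth?** The oral-liquid up-titration table in 10.4.2.1 is indexed by age and weight.

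- Cell for 3 months, 5 to below 7 kg: 50 mg. Against an equation dose of 26.2 mg (5.5 kg) to 27.8 mg (6 kg), this is 1.8 to 1.9 times, less than the 2.4-fold rise.
- Cell for 11 months, 9 to below 11 kg: 93.75 mg. Against the same 3-month equation dose, this is 93.75/27.8 = 3.4 to 93.75/26.2 = 3.6 times, more than the 2.4-fold rise.

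The answer depends on whether the table is read at entry or at current age and weight. The visible text does not say.

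**The case against.** The best defence is that 4.1.3 states an aim and then its operative rule, and that 5.7.1 is permissive and concerns timing: one adjustment, usable at any visit. On that view only loose wording is at issue. This stands in part, since 5.7.1 can be read that way. It does not dispose of a requirement to adjust over the whole study beside a per-patient cap, and it does not clearly settle what happens to a patient already adjusted who drifts.

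A reader might infer more: that infants will outgrow a single permitted increase of at most 2-fold and be removed from treatment for growing, so that 12-month on-drug data thin out selectively in the youngest group. The documents do not support this. Three objections to it hold:

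- The 2-fold ceiling relative to the entry dose is unproven, because the nomograms are indexed by age and weight.
- The target range is 5-fold wide (250/50), so a 2.4-fold rise does not by itself put a child out of range.
- The protocol gives no number of infants and no stopping rate from which a loss could be calculated. Discontinued patients also stay in follow-up and in the analysis population, so only on-drug exposure would be lost.

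Two further points are fair. Under a strictly enforced cap, nothing in the endpoint is hidden. And several nomogram figures are not shown, so a note on re-dosing there cannot be excluded.

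**Conclusion.** The conflict between 4.1.3 and 5.7.1 on one side and 7.3.2 on the other is real and needs no growth assumption. It leaves conflicting instructions for any patient adjusted into range who later drifts out, and it makes the secondary endpoint correct only if the cap is enforced everywhere.

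Growth shows where the gap is most likely to matter: a calculated-dose rise of about 2.4-fold over 12 months for entry at 3 months, 1.8- to 1.9-fold at 6 months, about 1.4-fold at 12 months, and about 1.1-fold at 8 or 12 years. These figures rest on assumed weights and on exposure proportional to dose over renal clearance. They show that drift is plausible in infants, not that one adjustment must fail or that infant data will be lost. The number of patients affected cannot be derived from the protocol.

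**What to change.** The sponsor must reconcile 4.1.3 and 5.7.1 with 3.3.4.1, 6.2.2 and 7.3.2, so that a patient who leaves the range after a successful adjustment falls under one consistent instruction. The text should also say at which age and weight the adjustment nomograms are read. Which clinical rule applies is for the sponsor; none is proposed here.

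In 7.3.2, report both the number of patients with at least one adjustment and the number of adjustments per patient, and tabulate trough-driven discontinuations by age group. The endpoint then counts what its name says, however the passages are reconciled.

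The cost is clarifying wording and one extra descriptive table. Section 4.1.2 already routes dose adjustments through the IRT.

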**Proprietary confidential information.**

© 2019 Boehringer Ingelheim International GmbH or one or more of its affiliated companies. All rights reserved.

This document may not - in full or in part - be passed on, reproduced, published or otherwise used without prior written permission.

For the reference patient, the equation giving the fractional dose is derived by taking the allometric equation for the GFR (equation 4 in [R06-2299](#)):

$$\text{GFR}(\text{age}, W) = 2.60 W^{0.662} e^{-0.0822 \cdot \text{age}} + 8.14 W^{0.662} (1 - e^{-0.0822 \cdot \text{age}}),$$

and subsequently dividing by weight (W) and by the weight-adjusted GFR of the comparator, 136mL/min / 70kg=1.94mL/min/kg. After rearranging, this results in the following equation for the fraction of the adult comparator mg/kg dose:

$$\text{FRAC} = W^{-0.338} (4.20 - 2.85 e^{-0.0822 \cdot \text{age}})$$

FRAC = fraction of adult comparator mg/kg dose

W = weight (kg)

Age (months)

The FRAC was further multiplied by 4.3 mg/kg (adult comparator BID mg/kg dose) and by the child's weight to obtain the absolute dose in mg. For weight groups (e.g. 5 and 6 kg) the average of the derived doses was used.

The derived dabigatran etexilate target doses based on Hayton calculations are displayed in [Table 4.1.3: 1](#). Please note that [Table 4.1.3: 1](#) does not contain information about age-appropriate formulations and available dose strengths. This information is given in the adjusted nomogram provided in [Appendix 10.4.1](#). Dosing of patients should only occur according to the adjusted nomogram provided in [Appendix 10.4.1](#).

